9.6 Pharmacodynamics

Details on the PD biomarker assessments are included

9.7 Pharmacogenomics

Not applicable.

Revised Protocol No.: 04 Date: 31-May-2019

Revised Protocol No.: 04 Date: 31-May-2019

9.9 Health Economics or Medical Resource Utilization and Health Economics

Health Economics or Medical Resource Utilization and Health Economics parameters will not be evaluated in this study.

10 STATISTICAL CONSIDERATIONS

10.1 Sample Size Determination

10.1.1 Preliminary Safety Cohorts and Dose Escalation (Part A)

Two single participants will be treated at BMS-986226 2 mg and 8 mg, respectively, in the Preliminary Safety Cohorts. Additional participants may be enrolled in the Preliminary Safety Cohorts at each dose level to gather additional information on the safety, PK, and PD profile. Approximately 3 participants will be treated at the starting dose levels of BMS-986226 in Part A. During the dose-escalation phase, an adaptive dose-escalation scheme (BLRM for monotherapy and BLRM-Copula for combination therapy) employing the escalation with overdose control (EWOC) principle will be used. The method is fully adaptive, makes use of all the information available at the time of each dose assignment, not just data from the current dose level, and directly addresses the ethical need to control the probability of overdosing. The targeted toxicity rate in this study is in the range of 16% to 33%. The boundary is similar to the toxicity boundary used by a rule-based design (ie, 3 + 3 design) in that a minimum is set at 16% (approximately 1 in 6) DLT rate and at a maximum at 33% (approximately 2 in 6) DLT rate. The use of the EWOC principle limits the risk of exposing participants in the next cohort to an unsafe dose by ensuring the posterior probability of the DLT rate exceeding 33% at any dose is capped at 30%.

Due to the nature of the dose escalation process, the exact number of participants to be treated at each dose level cannot be precisely determined. The maximum number of participants to be treated in Part A will be approximately 30 for dose escalation. However, simulation studies with various scenarios show that the expected number of DLT-evaluable participants is approximately 20 participants or less (Appendix 10).

While the BLRM/BLRM-Copula will use DLT information from the DLT period only, clinical assessment will take into consideration the totality of available data, including PK/PD from all treated participants encompassing monotherapy and combination therapy, in assigning a dose level for the next cohort of 3 participants. At most, 12 DLT-evaluable participants will be treated at each dose level. Additional participants (up to a total of 12) may be treated at or any dose level below the estimated MTD for further evaluation of safety, PK, or PD parameters as required.

The model-recommended MTD is the dose that satisfies the following 3 conditions:

- 1) The empirical posterior probability that the "DLT rate of 16% to < 33%" is greater than a prespecified value (ie, 50%);
- This probability needs to be the largest among the dose levels that satisfy the EWOC condition (ie, the probability that the "DLT rate > 33%" must be less than 30%);
- 3) The minimum number of participants (ie, 6 participants) was treated at this dose level.

The final recommended MTD/RP2D will be based on the recommendation from the BLRM/BLRM-Copula and the overall assessment of all available safety, PK/PD, and efficacy data. Lower doses of BMS-986226 may be tested if none of the planned doses are found to be tolerable as monotherapy or in combination with either nivolumab or ipilimumab. Such decisions will be made after discussion and agreement between the investigators and the BMS Medical Monitor/Study Director (or designee).

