During the dose-escalation phase, a set of approximately 3 participants will be treated initially at each specified dose level. Cohort tolerability assessment and subsequent dose recommendation will occur when at least 2 evaluable participants within a cohort have completed a 5-week DLT period. Any toxicities that occur beyond the 5-week DLT period will be accounted for in making dose level decisions and/or dose level modifications.

If the potential DLT occurring in the third evaluable participant regarding the specific dose level does not influence the dose recommendation by BLRM, the next dose level may proceed without waiting for the third participant to complete the corresponding DLT observation period after discussion and agreement between the Sponsor and investigators. Continuous re-assessment of dose recommendation, by BLRM in the monotherapy escalation phase, will be carried out for each dose level. Planned dose levels for dose escalation are provided in Table 5.1.2.1-1. Planned dose levels may be modified, or additional intermediate dose levels added, based upon the BLRM

analysis. Once the safety (during the DLT evaluation) of a monotherapy dose level has been established (Preliminary Safety Cohorts and Part A), additional participants (up to 12 total) may be added at that dose level to better characterize the safety, PK, and PD profile.

Dose Level	BMS-986226		
1	2 mg (Preliminary Safety Cohorts)		
2	8 mg (Preliminary Safety Cohorts)		
3	25 mg (Part A)		
4	80 mg (Part A)		
5	200 mg (Part A)		
6	400 mg (Part A)		
7	800 mg (Part A)		

 Table 5.1.2.1-1:
 Dose Escalation (Preliminary Safety Cohorts and Part A)

Dose-limiting Toxicities in Part A

For the purpose of guiding dose escalation, DLTs will be defined based on the incidence, intensity, and duration of AEs for which no clear alternative cause is identified. The DLT period will be 35 days (5 weeks) in Part A. Any toxicities that occur beyond the 5-week DLT period will also be considered in dose-level decisions.

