For the purpose of participant management, any AE that meets DLT criteria (Section 7.3.2), regardless of the cycle in which it occurs, will lead to discontinuation of study treatment. Participants who withdraw from the study during the DLT evaluation period for reasons other than a DLT may be replaced with a new participant at the same dose level. The incidence of DLT(s) during the DLT evaluation period will be used in dose escalation decisions in Part A and guide dose recommendations in Parts B and C. AEs occurring after the 5-week DLT evaluation period will be considered for the purposes of defining any BLRM recommended dose upon agreement between the Sponsor, Medical Monitor/Study Director (or designee), and investigators, if the AEs are determined to have no clear alternative cause and are not related to disease progression.

AEs will be graded according to the National Cancer Institute (NCI) Common Terminology Criteria for Adverse Events (CTCAE) v4.03.²⁷

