7.3.2 BMS-986226 Dose-limiting Toxicities

For the purpose of guiding dose escalation, DLTs will be defined based on the incidence, intensity, and duration of AEs for which no clear alternative cause is identified. The DLT period will be 35 days (5 weeks).

In the Preliminary Safety Cohorts, participants who have received 1 dose of BMS-986226 and have completed, or who discontinued due to a DLT in the 4-week DLT period, will be considered as DLT-evaluable participants for BMS-986226 monotherapy.

In Part A, participants who have received 2 doses of BMS-986226 and have completed, or who discontinued due to a DLT in the 5-week DLT period, will be considered as DLT-evaluable participants for BMS-986226 monotherapy.

In Parts B, C, D and E, participants receiving either 1 dose of BMS-986226 or 2 doses of either nivolumab or ipilimumab, or participants who discontinued due to a DLT in the 5-week combination treatment DLT period, will be considered as DLT-evaluable participants for combination treatment. Participants who withdraw from the study during the DLT evaluation period or have received less than 2 doses for reasons other than a DLT in the monotherapy (Part A) or 1 dose in combination therapy (Parts B, C, D, E), will not be considered as DLT-evaluable participants in Part A, who are dose delayed during the DLT evaluation period for reasons other than a DLT could be considered as DLT-evaluable participants if they receive at least 2 doses of therapy.

For the purpose of participant management, any AE that meets DLT criteria, regardless of the cycle in which it occurs, will lead to discontinuation of study treatment (except as defined in Section 7.3.5). Participants who withdraw from the study during the 5-week DLT evaluation period for reasons other than a DLT may be replaced with a new participant at the same dose

level. The incidence of DLT(s) during the 5-week DLT evaluation period will be used in dose escalation decisions through application of the BLRM/BLRM-Copula model. AEs occurring after the DLT period will be considered to enhance the robustness of BLRM/BLRM-Copula prediction, upon agreement between the Sponsor, Medical Monitor/Study Director (or designee), and investigators.

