Participants experiencing a DLT will enter the safety follow-up period of the study. DLTs occurring after the 4-week DLT observation period for the Preliminary Safety Cohorts or 5-week DLT observation period for Parts A, B and C will be accounted for in determining the MAD for the combination part.

AEs will be graded according to the NCI CTCAE v4.03²⁷, as listed below:

A. Hepatic Non-hematological DLT

Any one of the following study treatment-related events will be considered a hepatic DLT:

- Any Grade \geq 3 elevation of AST, ALT, or total bilirubin.
- Grade 2 AST or ALT with symptomatic liver inflammation (eg, right upper quadrant tenderness, jaundice, pruritus).
- AST or ALT > 3× ULN and concurrent total bilirubin > 2× ULN without initial findings of cholestasis (elevated serum alkaline phosphatase [ALP] [eg, findings consistent with Hy's law or FDA definition of potential drug-induced liver injury or potential drug-induced liver injury [p-DILI]). Note that this special category of DLT uses ULN rather than Common Toxicity Criteria (CTC) grade for definition.

B. Non-hepatic Non-hematological DLT

Any of the following events will be considered a non-hepatic non-hematological DLT:

- Any Grade 2 drug-related uveitis or eye pain or blurred vision that does not respond to topical therapy and does not improve to Grade 1 severity ≤ 2 weeks *or* requires systemic treatment.
- Grade 3 drug-related uveitis, pneumonitis, bronchospasm, myocarditis, neurologic toxicity, hypersensitivity reaction, or infusion reaction of any duration will require discontinuation.
- Any Grade 3 or greater nondermatologic, nonhepatic nonhematological study treatment-related toxicity will be considered a DLT, with the following specific exceptions:
 - Grade 3 or Grade 4 electrolyte abnormalities that are not complicated by associated clinical adverse experiences, last \leq 72 hours, and either resolve spontaneously or respond to conventional medical intervention
 - Grade 3 nausea, vomiting, or diarrhea that lasts less than 72 hours (without steroid therapy) and either resolves spontaneously or responds to conventional medical intervention
 - Isolated Grade 3 elevation of amylase or lipase not associated with clinical or radiographic evidence of pancreatitis

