1 MODEL SETUP FOR BMS-986226 MONOTHERAPY

1.1 Monotherapy Methodology Description

An adaptive 2-parameter Bayesian Logistic Regression Model (BLRM) guided by the escalation with overdose control (EWOC) principle^{1,2,3} will be used to guide the dose escalation of BMS-986226 monotherapy in the monotherapy phase, providing dose recommendation during dose escalation.

The BLRM will be fitted on the dose-limiting toxicity (DLT) data during the first 5 weeks of treatment accumulated throughout the dose escalation to model the dose-toxicity relationship of BMS-986226 in the monotherapy dose escalation phase.

The dose-toxicity relationships for BMS-986226 monotherapy is assumed to follow a logistic model:

$$logit(p_i) = log(\alpha_1) + \beta_1 log(\frac{d_{1i}}{d_1^*}),$$

where p_i is the probability of toxicity at dose level d_{1i} . Note that the α_1 and β_1 parameters are assumed positive, and d_1^* is the reference dose for BMS-986226 (please refer to the meaning of α_1 and β_1 in Section 1.2 for detailed implementation).

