2 DECISION RULE FOR DOSE ESCALATION AND SIMULATION

Dose escalation recommendations for BMS-986226 monotherapy will be based on the inference from the Bayesian posterior and the probability that the true DLT rate for each dose lies in 1 of the following categories:

- [0%, 16%) under-dosing
- [16%, 33%) targeted toxicity
- [33%, 100%] excessive toxicity

Note: "[" or "]" is inclusive of the respective endpoint, and "(" or ")" exclusive of the respective endpoint.

These boundaries are similar to the toxicity boundaries used by a rule-based design (ie, 3 + 3 design) in that a minimum is set at 16% (~ 1 in 6) DLT rate and a maximum at 33% (~ 2 in 6) DLT rate. Following the principle of EWOC, dose recommendations for the next cohort will be based on the Bayesian model after DLT information becomes available during the DLT period, accounting for all of the available data from the administered doses, and the candidate doses are the ones fulfilling the overdose criterion that there is less than 30% chance of excessive toxicity. Only the candidate doses will be considered for the next cohort. While the Bayesian model will use DLT information from the DLT period only, clinical assessment will take into consideration of the totality of available data including pharmacokinetics (PK)/pharmacodynamics from all treated participants.

Stopping Rules:

The following is the general stopping rules of BLRM (-Copula) during Dose Escalation:

• If all of 30 DLT evaluable participants are treated.

- If all of the current pre-specified doses are considered intolerable according to the pre-specified cutoff (ie, EWOC criteria), then the model will recommend stopping the current dose level and a new dose level lower than the current lowest dose level will need to be identified.
- The maximum number of DLT-evaluable participants in a dose level will be 12. This limit is set to avoid instances in which the model could recommend adding subjects indefinitely to a specific dose level due to uncertainty in the tolerability profile.
- If, for a specific dose level, 6 subjects have been treated and the chance of determining that the dose level to be the "target" dose is > 50%, then the model will suggest to stop and declare the current dose level to be the maximum tolerated dose (MTD).

Model-recommended MTD:

The MTD is the dose that satisfies the following 3 conditions:

- 1) The empirical posterior probability that the 'DLT rate of 16% -< 33%' is greater than 50%.

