5 DOSE RECOMMENDATION BY BLRM-COPULA FOR BMS-986226 IN COMBINATION COHORTS

Similar to the dose escalation recommendation for BMS-986226 monotherapy, any recommended dose by BLRM Copula (for Parts B and C, and not to exceed the maximum administrated dose of the BMS-986226 monotherapy in Part A) and any potential dose recommendation for the combination cohorts will be based on the inference from the Bayesian posterior and the probability (obtained from the BLRM-Copula model) that the true DLT rate for each dose lies in 1 of the following categories:

- [0%, 16%) under-dosing
- [16%, 33%) targeted toxicity
- [33%, 100%] excessive toxicity

While the Bayesian model will use DLT information of all available data from the DLT period only, clinical assessment will take into consideration of the totality of available data including PK/PD from all treated participants.

BLRM-Copula Model-Recommended Dose:

At any time a dose recommended by BLRM-Copula model for BMS-986226, using all available data to date and time, is the dose that satisfies the following conditions:

- 1) Not to exceed the maximum administrated dose of BMS-986226 in Part A, ie., the BMS-986226 monotherapy phase
- 2) This probability of the true DLT rate falling into the targeted toxicity interval, i.e., [16%, 33%), needs to be the largest (or be comparable to numerically the largest with negligible practical difference) among the dose levels that satisfy the EWOC condition (ie, the probability that 'DLT rate ≥ 33%') must be less than 30%;

Final BLRM-Copula Recommended Dose:

Any final recommended BLRM-Copula recommended dose will be based on the recommendation from the BLRM-copula and overall clinical assessment of all available safety, PK/PD, and efficacy data. Also, note that the dose recommendation by BLRM-Copula is a real-time on-going process, and can be done whenever new DLT information is available.

6 **REFERENCES**

- ¹ Babb J, Rogatko A, Zacks S. Cancer Phase I clinical trials: efficient dose escalation with overdose control. Stat Med 1998;17:1103-20.
- ² Neuenschwander B, Branson M, Gsponer T. Critical aspects of the Bayesian approach to Phase I cancer trials. Stat Med 2008;27:2420-39.
- ³ Neuenschwander B, Capkun-Niggli G, Branson M, et al. Summarizing historical information on controls in clinical trials. Clin Trials 2010;7:5-18.
- ⁴ Yin G, Yuan Y. Bayesian dose finding in oncology for drug combinations by copula regression. J R Stat Soc Ser C Appl Stat 2009;58(2):211-24.

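### The plan confines the BLRM to DLT-period data but also lets later adverse events into its prediction by agreement; on some Part A paths that choice decides whether 800 mg meets the 30% overdose limit.

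*Combined protocol and SAP*

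**What the plan says.** Three places restrict the model's input. Section 10.1.1 has "While the BLRM/BLRM-Copula will use DLT information from the DLT period only" and leaves the totality of the data to clinical assessment. Appendix 10, Section 2 says the same for monotherapy. Appendix 10, Section 5 repeats it for the combinations: "While the Bayesian model will use DLT information of all available data from the DLT period only". Appendix 10, Section 1.1 describes the fit consistently, though without the word only: "The BLRM will be fitted on the dose-limiting toxicity (DLT) data during the first 5 weeks of treatment".

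Section 7.3.2 points the other way: "AEs occurring after the DLT period will be considered to enhance the robustness of BLRM/BLRM-Copula prediction, upon agreement between the Sponsor", the medical monitor or study director, and the investigators. Section 5.1.2.1 has a related sentence for Part A: "AEs occurring after the 5-week DLT evaluation period will be considered for the purposes of defining any BLRM recommended dose upon agreement" among the same parties. It adds two conditions: the event has no other evident cause and is not attributable to progression.

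Separately from the model, the plan requires late toxicity to be weighed. Section 5.1.2.1 says "Any toxicities that occur beyond the 5-week DLT period will be accounted for in making dose level decisions and/or dose level modifications". Section 7.3.2 says late DLTs "will be accounted for in determining the MAD for the combination part".

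The model output has a formal role. Appendix 10, Section 2 defines candidate doses as those with less than a 30% chance of a DLT rate of 33% or more, and states: "Only the candidate doses will be considered for the next cohort".

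**The concern.** The 30% limit is the plan's stated protection against overdosing, and Section 5.1.6 says there is no data monitoring committee. A limit of this kind should give one answer for one set of data. Here the answer can depend on whether Section 7.3.2 or Section 10.1.1 is followed, and under Section 7.3.2 that is settled after the event has been seen.

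The discretion also works in both directions. A late event at or near the current dose raises the predicted risk at 800 mg. A late event at a low dose flattens the fitted dose-toxicity slope and can lower that risk, so adding a toxicity can admit a dose that the in-window data exclude.

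Late events are foreseeable. Part A gives up to six doses at 28-day intervals, on Days 1, 29, 57, 85, 113 and 141. Only the first two fall inside the 35-day window.

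**Working it through.** **Inputs.** Appendix 10, Sections 1.1 and 1.2: logit(p) = log(α) + β·log(d/800), with log(α) ~ N(−0.847, 1.53²), log(β) ~ N(0, 1²) and correlation 0. Section 2: excessive toxicity is p ≥ 0.33, the target interval is 0.16 to below 0.33, and a dose is a candidate if P(p ≥ 0.33) < 0.30. Section 2.1: doses 25, 80, 200, 400 and 800 mg, cohorts of 3. The likelihood is binomial, and the posterior was obtained by grid integration and confirmed by importance sampling.

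**Assumed, because the plan gives no method.** A late event turns one participant already counted as DLT-free into a DLT, with the denominator unchanged. It is known before the next dose opens unless stated.

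**The plan's own example first.** Appendix 10, Section 3 takes 0/3 at 25 mg and 1/3 at 80 mg and prints target probabilities of 0.372 at 200 mg and 0.311 at 80 mg, with 400 and 800 mg excluded. The refit gives 0.360 and 0.299, with overdose probabilities of 0.284 (200 mg), 0.468 (400 mg) and 0.631 (800 mg). The exclusions and the recommendation of 200 mg agree. The gap is 0.372 − 0.360 = 0.012, so results within about 0.02 of the limit are not counted as crossings.

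**P(DLT rate ≥ 33%) at 800 mg, limit 0.30**

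| In-window data | Late event left out | Late event entered | 800 mg |
|---|---|---|---|
| 0/3 at 25, 80, 200, 400 mg | 0.218 | at 400 mg: 0.478 | admitted, then excluded |
| same | 0.218 | at 200 mg: 0.351 | admitted, then excluded |
| same | 0.218 | at 25 mg: 0.188; at 80 mg: 0.255 | admitted either way |
| 0/3 at 25, 80, 200 mg; 2/12 at 400 mg | 0.388 | at 25 mg: 0.219 | excluded, then admitted |
| 0/6 at 25, 80, 200 mg; 1/6 at 400 mg | 0.354 | at 25 mg: 0.173 | excluded, then admitted |
| same | 0.354 | at 80 mg: 0.278 | excluded, then admitted by a small margin |
| 0/3 at 25, 80, 200 mg; 1/6 at 400 mg | 0.359 | at 25 mg: 0.270 | excluded, then admitted |

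**Recommendation as well as admission.** On the 0/6 path with the event at 25 mg, the target probability is 0.436 at 800 mg against 0.362 at 400 mg, so the model would recommend 800 mg. On the 2/12 path it is 0.532 against 0.509. There 800 mg has the larger value, but 0.509 also passes the 50% stopping criterion for 400 mg, so the 0/6 path is the cleaner illustration. On the 1/6 path with three per lower dose it is 0.465 against 0.469, in effect a tie.

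**Reachability of the 2/12 path.** With 0/3 at each lower dose, 1/3, 1/6, 2/9 and 2/12 at 400 mg give 0.478, 0.359, 0.477 and 0.388 at 800 mg. All exceed 0.30, so the in-window rule keeps enrolment at or below 400 mg throughout, and 12 is the permitted maximum at one dose.

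**Where nothing changes.** With three at each lower dose and nine at 400 mg, a late event at 400 mg gives 0.284. If the event at 400 mg is known only after 0/3 at 800 mg, the figure is 0.170. With three per lower dose and 1/6 at 400 mg, an event at 80 mg leaves 800 mg excluded at about 0.35.

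**Preliminary Safety Cohorts.** Adding 0/1 at 2 mg and 0/1 at 8 mg changes the table's crossing figures by at most 0.004 and reverses none.

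**The case against.** The strongest reply is that Sections 7.3.2 and 5.1.2.1 describe clinical judgement laid over the model output. Section 5.1.2.1 can fairly be read that way. Section 7.3.2 is harder to read so, because it speaks of the prediction of the BLRM/BLRM-Copula itself and the plan states the clinical overlay elsewhere.

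A second reply is that the crossings are selective. That stands in part. The event at 200 mg on the 0/3 path no longer crosses with four per cohort (0.284). In a coarse enumeration of 2,609 model-following states, about 88 (88/2609 = 3.4%) crossed upward and 38 (38/2609 = 1.5%) downward, unweighted by likelihood. The crossing with an event at 400 mg is sturdier, but the event must surface after Day 35 and before 800 mg opens.

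A third reply is that the model only guides escalation. That also stands: the dose decision rests on review of safety, PK and PD data with investigators (Section 5.1.6), and meeting the limit compels nothing.

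A reader might infer that the plan ignores late toxicity, or that it sets no conditions on late events. Neither is supported: Sections 5.1.2.1 and 7.3.2 require late toxicity to be weighed, and Section 5.1.2.1 sets two conditions.

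**Conclusion.** The plan is inconsistent as written. Sections 10.1.1 and Appendix 10 (Sections 2 and 5) confine the model to DLT-period data; Section 7.3.2 lets later events into its prediction by agreement after the fact; and neither coding nor precedence is given. On some Part A paths one late event moves 800 mg across the 30% limit: upward from 0.22 to 0.48, or downward from 0.39 to 0.22 and from 0.35 to 0.17.

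This rests on the protocol's prior, the assumed cohort sizes and event positions, and coding a late event as a DLT with the denominator unchanged. It would be wrong to infer that any late event changes the result, that an unsafe escalation would follow, or that one event has been shown to cross the limit in the combinations. The crossings depend on path and cohort size, clinical review still applies, and no single-event crossing was established for Parts B and C. It should be fixed because it concerns a safety limit and costs little.

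**What to change.** Amend Section 7.3.2 and the matching sentence in Section 5.1.2.1 so that the fit used for the 30% limit takes in-window DLTs only and late events are never entered by case-by-case agreement. A late event then cannot admit a dose that the in-window fit excludes. Keep the clinical review of late toxicity unchanged.

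At each update also report a prespecified sensitivity fit. It should code as a DLT every post-window event that meets the Section 7.3.2 criteria, has no clear alternative cause and is not due to progression. The dose review should consider it as a possible reason not to escalate and never as a reason to escalate.

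Requiring a dose to pass both fits is optional. It should be simulated first, because its operating characteristics are unknown and the coding ignores unequal follow-up: early leavers count as event-free, and the lower-dose cohorts are observed longest.

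The cost is wording in two sections and one extra model run per update, with no added participants or assessments. Escalation may be slower after a late event.
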